9.4.3. Analyses of Secondary Endpoints

All secondary and exploratory efficacy analyses on endpoints evaluated as change from Baseline, for both EMA and non-EMA regions, will follow treatment policy strategy regardless of treatment discontinuation or death. Binary endpoints indicated for responder analyses will follow an estimand elaborated below for UHDRS-TFC response.

Multiplicity Adjusted Secondary Endpoints:

The key secondary efficacy variable is change from Baseline to Week 65 in cUHDRS and the main estimand is defined similarly to non-EMA-Estimand for primary endpoint as described in Section 3.1.2. Change from Baseline to Week 65 in cUHDRS will be analyzed using the MMRM in mITT population under treatment policy strategy, as described for the primary endpoint in Section 9.4.2. Other multiplicity adjusted secondary endpoints (UHDRS-TMS, Q-Motor [REDACTED] and SDMT), evaluated as change from Baseline to post-baseline visits, will also be analyzed similarly to cUHDRS.

The binary UHDRS-TFC response at Week 65 is defined as achieving improvement or no worsening in UHDRS-TFC score, i.e., change from Baseline to Week 65 ≥ 0 points. The hypothesis testing is based on the main estimand as follows:

- Treatment: Pridopidine 45 mg bid or placebo (on background of standard of care) that participants are randomized to
- Population: Early HD Participants (HD1 & HD2) defined through the study inclusion/exclusion criteria. The mITT population will be used in analyzing this estimand
- Variable: Improvement or no worsening (change from Baseline ≥ 0 point) at Week 65 in UHDRS-TFC (Defined as responders to treatment)
- Population Level Summary: Proportion of responders, defined as the proportion of participants achieving improvement or no worsening in UHDRS-TFC (change from Baseline ≥ 0 point) at Week 65
- ICEs and Strategies for Addressing ICEs:

ICEs include treatment discontinuation and will be handled by combining composite strategy and hypothetical strategy as follows:

- Composite strategy: Observed UHDRS-TFC values will be used to determine if a participant is a responder or not. For treatment discontinuation due to disease-progression-related death, or meeting Stopping Rules, the participant will be considered a non-responder.

Hypothetical strategy: For treatment discontinuation due to other reasons not included in composite strategy and no TFC data collected afterward, all values after ICEs will be imputed

under MAR as if the participants had continued receiving the study treatment. The MAR imputation model will include UHDRS-TFC as a continuous response variable as described in Section 9.4.2. The UHDRS-TFC response at Week 65 (change from Baseline in UHDRS-TFC \geq 0) will then be derived using the imputed UHDRS-TFC score as well as the non-missing UHDRS-TFC scores.

The proportion of participants with improvement or no worsening based on CGI-C (assessed as \geq 1 and \leq 4), will be analyzed using a logistic regression in the mITT population, as described above for binary UHDRS-TFC response.

Non-Multiplicity Adjusted Secondary Efficacy Endpoints:

The continuous non-multiplicity adjusted secondary endpoints (change from Baseline to post-baseline visits in UHDRS-TMS, Q-Motor [REDACTED] and cUHDRS total score) will be analyzed similarly as described in non-EMA-Estimand for the primary endpoint.

Q-Motor endpoints [REDACTED]

The binary non-multiplicity adjusted secondary endpoints, evaluated as proportion of participants meeting a given threshold, will be analyzed similarly to UHDRS-TFC response. Different thresholds that are clinically meaningful may be used for the responder analyses.

Further details for secondary analyses will be included in the SAP.

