9.3.1. Main Study

Population	Description
Intent-to-Treat (ITT) population	The ITT population will include all randomized participants. The participants will be grouped as randomized.
Modified Intent-to-Treat (mITT) population	The mITT set is a subset of the ITT population and will include all randomized participants who receive a dose of study drug and have valid TFC efficacy assessments both at the Baseline visit and at least one post-baseline in-clinic timepoint. The participants will be grouped as randomized.
Per Protocol Week 65 (W65PP) population	The per protocol Week 65 set is a subset of the mITT set and includes all participants who have a valid in-clinic UHDRS-TFC at Week 65, were on study drug with compliance > 80% during the study, and did not have any important protocol deviations impacting efficacy assessment. Per protocol variations will be defined prior to unblinding the data and participants subsequently grouped as treated. The per protocol set will be used for supplementary analysis of the primary and select secondary endpoints.
Per Protocol Week 78 (W78PP) population	The per protocol Week 78 set is a subset of the mITT set and includes all participants who have a valid in-clinic UHDRS-TFC at Week 78, were on study drug with compliance > 80% during the study, and did not have any important protocol deviations impacting efficacy assessment. Per protocol variations will be defined prior to unblinding the data and participants subsequently grouped as treated. The per protocol set will be used for supplementary analysis of the primary and select secondary endpoints.
Safety population	The safety set will include all participants receiving at least one dose of study drug. The participants will be grouped according to the treatment regimen actually received. The safety set will be used for safety analyses.
PK population	The PK population will include all randomized participants who received at least 1 dose of pridopidine and have at least 1 valid PK assessment. The

Population	Description
	participants will be grouped according to the treatment regimen actually received.

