10.8. Appendix 8: ECG Monitoring Plan

ECG Monitoring Flow

During in-clinic visits:

For all participants, ECG will be administered at Screening, Baseline, Week 4 (V3), Week 26 (V4) and Week 65 (V7).

At Screening, a single 12-lead ECG will be administered to assess eligibility.

At Baseline (V2) Visit:

- A triplicate 12-lead ECG will be administered BEFORE 1st drug administration to determine the participant baseline QTcF.
- A single 12-lead ECG will also be administered 1-2 hours POST 1st drug administration.

At Week 4 (V3), a single 12-lead ECG will be administered 1-2 hours post-study drug administration.

At Week 26 (V4) and Week 65 (V7), and Week 78 (V8/EoS/ET) for participants not continuing to OLE a single 12-lead ECG will be administered before study-drug administration.

[figure not shown]
1. Screening Visit (V1)

- QTcF will be measured by a single 12-lead ECG administration
- If the QTcF is >450 ms for men and >470 ms for women, then ECG will be repeated twice¹¹ and the QTcF will be determined by the average of the 3 ECGs
- If mean QTcF is >450 ms for men and >470 ms for women, then the participant will screen fail and will not be randomized

2. Baseline Visit (V2) ECG will be administered **before** first study drug administration:

- QTcF will be measured by a mean of 3 12-lead ECG administrations (triplicate)
- 2. Baseline Visit (V2) and Week 4 (V3), single 12-lead ECG will be administered **1-2 hours post-study drug administration** ([Figure 3](#))
- 3. Week 26 and 65 visits or ET, single 12 lead ECG will be administered **before** study drug administration ([Figure 3](#))

¹¹ Standard ECG administration for abnormal QTcF readings will be for the ECG to be repeated twice (at least 5 minutes after the 1st ECG, and with an interval of at least 1 minute between each of the 2 additional 10-second recordings), and the mean of the 3 screening administrations will be used to determine final QTcF.

Figure 3: ECG Monitoring Flow

- QTcF will be measured by a single 12-lead ECG
- If QTcF meets Stopping/Monitoring Rules, then ECG will be repeated twice¹² and the QTcF will be determined by the average of the 3 ECGs
- If the average QTcF meets Stopping Rules (confirmed by central read ECG), then the participant is withdrawn from study drug and a follow-up ECG will be performed as soon as practicable (after 2 days) to ensure recovery from QT prolongation

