4.1.2. Modified Intent-to-Treat (mITT) Population

The modified intent-to-treat (mITT) population is a subset of the ITT population and will include all participants in the ITT population who received at least 1 dose of study drug and have valid in-clinic TFC scores both at Baseline and at least 1 post-baseline timepoint. The mITT population will be analyzed according to the treatment to which the participant was randomized. The mITT population is the main analysis population for primary endpoint in non-EMA submission. For all other efficacy analyses, the mITT population is the main analysis population in both EMA and non-EMA submission.

All participants who received at least 1 dose of pridopidine and have at least 1 valid in-clinic UHDRS-TFC score during the OLE period will be included in the OLE mITT population.

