6. STUDY POPULATION

6.1. Participant Disposition

For Main Study analyses, all references to participant disposition, etc., refer only to the Main Study and exclude the OLE.

The number of participants who signed informed consent, or signed consent but were not randomized along with reason for screening failure will be summarized overall and by region and for select countries.

The number of participants included in each analysis population will be presented by treatment group. The participants who are excluded from each of the analysis population and the reason for exclusion (for example, exclusion from mITT population because they were not treated, or if they were treated but have no post-baseline in-clinic UHDRS-TFC assessment), will be summarized by treatment group. These participants will be identified in the listing of participants with populations in which they are included.

The end of the Main Study is reached when all participants who have signed informed consent, been randomized and treated have either completed through Week 65 or discontinued from the study (defined in Section 5.5.5). At the end of Main Study, the number of participants who completed the Main Study portion as well as those that withdraw from the treatment or study will be summarized along with the reason for withdrawal. The denominator for calculating the percentages will be the number of participants within the treatment group in the population being summarized.

In the OLE analyses, the numbers of participants who have enrolled in the OLE portion, who are included in each analysis population, who have completed the OLE, and who withdraw from the treatment or study along with the reasons will be summarized.

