7.4.2. UHDRS-TFC Response as a Binary Endpoint

The binary UHDRS-TFC response (yes or no) is defined as achieving improvement or no worsening in UHDRS-TFC score, i.e., change from Baseline to Week 65 in UHDRS-TFC ≥ 0

points. The responder analysis will be performed for the proportion of participants with change from baseline to Week 65 in UHDRS-TFC ≥ 0 .

The hypothesis testing to compare the percentage of responders between the two treatment groups will be based upon the mITT population. Logistic regression will be used to analyze and compare the probability of whether a participant is a UHDRS-TFC responder or not. The model will adjust for Baseline UHDRS-TFC, region, Baseline randomization stratification factors of neuroleptic use (Yes/No) and HD stage (HD1 and HD2).

The hypothesis testing of the UHDRS-TFC responder analysis is based on the main estimand as follows:

- Treatment: Pridopidine 45 mg bid or placebo (on background of standard of care) that participants are randomized to
- Population: Early HD Participants (HD1 & HD2) defined through the study inclusion/exclusion criteria. The mITT population will be used in analyzing this estimand
- Variable: Improvement or no worsening (change from Baseline ≥ 0 points) at Week 65 in UHDRS-TFC (Defined as responders to treatment)
- Population Level Summary: Proportion of responders, defined as the proportion of participants achieving improvement or no worsening in UHDRS-TFC (change from Baseline ≥ 0 points) at Week 65
- ICEs and Strategies for Addressing ICEs:

ICEs include treatment discontinuation and will be handled by combining composite strategy and hypothetical strategy as follows:

- Composite strategy: Observed UHDRS-TFC values will be used to determine if a participant is a responder or not. For treatment discontinuation due to disease-progression-related death, or meeting Stopping Rules, the participant will be considered a non-responder.
- Hypothetical strategy: For treatment discontinuation due to other reasons not included in composite strategy and no TFC data collected afterward, all values after ICEs will be imputed under MAR as if the participants had continued receiving the study treatment. The MAR imputation model will include UHDRS-TFC as a continuous response variable as described in Section 7.2. The UHDRS-TFC response at Week 65 (change from Baseline in UHDRS-TFC ≥ 0) will then be derived using the imputed UHDRS-TFC score as well as the non-missing UHDRS-TFC scores.

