The odds ratio (OR) of treatment effect (pridopidine 45 mg bid vs placebo) along with a 2-sided 95% CI and p-value will be presented. An estimate of OR > 1 will indicate a beneficial treatment effect. Descriptive statistics and 95% CI using Clopper-Pearson will be provided for the observed proportions at each visit, along with the difference between treatment groups in the proportions and 95% normally approximated CI for the difference.

Following supportive estimands will be used to support the analysis of this secondary endpoint:

Supportive Estimand 1: similarly defined as the main estimand for UHDRS-TFC responder analysis, but with population changed to ITT population, and MNAR instead of MAR MI will be used under the hypothetical strategy.

Supportive Estimand 2: similarly defined as the main estimand for UHDRS-TFC responder analysis, but with population changed to ITT population.

Supportive Estimand 3: similarly defined as the main estimand for UHDRS-TFC responder analysis, but with ICE handling strategy changed to treatment policy strategy (using observed data without imputation).

Supportive Estimand 4: similarly defined as Supportive Estimand 3 for UHDRS-TFC responder analysis, but with population changed to W65PP population.

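### The main responder analyses are run in mITT, so an early composite failure with no post-baseline in-clinic TFC is dropped instead of counted as a non-responder

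*Protocol*

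**What the plan says.** The main estimand for TFC response at Week 65 (change from Baseline of at least 0) is the same in Protocol 9.4.3 and SAP 7.4.2. Its composite part reads: "For treatment discontinuation due to disease-progression-related death, or meeting Stopping Rules, the participant will be considered a non-responder". Other discontinuations with no later TFC are imputed under MAR.

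The analysis set is mITT. SAP 7.4.2: "The hypothesis testing to compare the percentage of responders between the two treatment groups will be based upon the mITT population". Under Protocol 9.3.1 these participants must be dosed and "have valid TFC efficacy assessments both at the Baseline visit and at least one post-baseline in-clinic timepoint". SAP 4.1.2 matches: participants who "received at least 1 dose of study drug and have valid in-clinic TFC scores both at Baseline and at least 1 post-baseline timepoint".

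SAP 6.1 foresees the excluded group. Its example of a reason for exclusion from mITT covers participants not treated, or "if they were treated but have no post-baseline in-clinic UHDRS-TFC assessment". Exclusions are to be summarised by arm with reasons.

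SAP 7.4.3 applies the same main estimand and set to the other binary endpoints, including CGI-C response at Week 65, and takes the p-values for the hierarchy from the main estimand. For TFC response, SAP 7.4.2 also plans Supportive Estimand 2, which is "similarly defined as the main estimand for UHDRS-TFC responder analysis, but with population changed to ITT population".

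**The concern.** The composite strategy makes certain exits an outcome. Once a dosed participant has stopped under a Stopping Rule or died of disease progression, the response value is known to be no, and no later measurement is needed. The mITT condition adds a measurement requirement that the estimand does not have, so a participant whose outcome is known can be removed for lack of data that would not be used.

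The time at risk is before the first post-baseline in-clinic TFC, scheduled at Week 26. Post-dose ECGs at Baseline and Week 4, Week 4 laboratory tests and several C-SSRS checks come earlier, so a Stopping Rule can be met in that window.

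At stake are two endpoints in the confirmatory sequence, TFC response (#2) and CGI-C response (#9). Because the hierarchy uses the main-estimand p-value, the planned ITT version cannot correct the formal result. For CGI-C, inclusion also depends on a different instrument, the TFC.

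**Working it through.** **Who is lost.** Setting the provisions side by side:

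- The mITT definition asks for any post-baseline in-clinic timepoint, not a scheduled visit.
- A participant who stops drug but stays in the study should first have an ET visit (Schedule of Activities, footnote g). The V8/ET column includes UHDRS-TFC. Protocol 7.2 does not allow the ET visit to be replaced by phone. SAP 5.5.3 assigns ET data to a scheduled visit for efficacy models. Such a participant is in mITT and counts as a non-responder.
- Three gaps remain. No ET visit is possible after death. On withdrawal, ET procedures are required only where possible (Protocol 7.3). Off-drug participants may replace the Week 4, 26, 39 and 52 clinic visits by phone, and TFC is then not assessed (Protocol 7.2; Table 8 footnote), so after a missed ET visit the next in-clinic TFC may be Week 65.

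**Inputs.** 240 per arm (SAP 3.1). The documents state no response rate, power or count of early exits for the responder endpoint, so there is no plan figure to reproduce here. The primary-endpoint power figures are not affected. Assumed: p = response rate among those retained, equal in both arms, 0.3 to 0.6; f = share of an arm that meets the composite rule and has no post-baseline in-clinic TFC, 0 to 2%.

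**Formula.** With the lost failures counted, an arm's rate is p × (1 − f); in mITT it is p. The bias in the risk difference (pridopidine minus placebo) is therefore p × (fA − fP).

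| fA | fP | p = 0.3 | p = 0.5 | p = 0.6 |
|---|---|---|---|---|
| 1% | 0 | +0.3 points | +0.5 | +0.6 |
| 2% | 0 | +0.6 | +1.0 | +1.2 |
| 2% | 1% | +0.3 | +0.5 | +0.6 |
| 2% | 2% | 0 | 0 | 0 |
| 1% | 2% | −0.3 | −0.5 | −0.6 |

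A positive sign favours pridopidine.

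**Effect of the ET visit.** Suppose 2% of the pridopidine arm fails early (240 × 0.02 = 4.8 participants), none on placebo, and p = 0.5. If 80% attend ET, 4.8 × 0.2 = 0.96 participants are dropped and the bias is 0.5 × 0.02 × 0.2 = 0.002, or 0.2 points.

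**Effect on the test.** Let the true rate with failures counted be 0.5 in both arms, with 2% lost on pridopidine only.

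- mITT rate on pridopidine: 0.5 / 0.98 = 0.5102, on 235.2 participants. On placebo: 0.5, on 240.
- Difference 0.0102; SE = √(0.5102 × 0.4898 / 235.2 + 0.25 / 240) = 0.0459; ratio 0.222.
- Chance of a false positive favouring pridopidine: P(Z > 1.96 − 0.222) = 4.1%, against 2.5% nominal. Two-sided rejection is 5.6%.

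**The case against.** A reader might infer that early failures are deleted as a rule, because the first scheduled TFC is at Week 26. The documents do not support that: a participant who follows the protocol after a Week 4 Stopping Rule has an in-clinic ET visit with TFC and is counted. The objection stands, and it limits the point to deaths and to participants with no ET or later in-clinic TFC.

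A reader might also infer that the omission favours pridopidine, since QT prolongation and reduced creatinine clearance are stated risks (Protocol 2.3.1). That direction is plausible but not shown. No early-exit rates by arm are given. The stated QTcF effect at the trial dose is 6.6 ms, which the protocol does not regard as clinically meaningful. The psychiatric rule and deaths can occur in either arm. Balanced losses give no bias, and an excess on placebo reverses it.

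The size is also modest. With 240 per arm and p = 0.5, the SE of the difference is √(2 × 0.25 / 240) = 4.6 points, so a 1-point bias is about 0.2 SE. SAP 3.6.3.1 reports a low discontinuation rate and 98.9% completion of in-clinic TFC, which suggests small numbers, although neither figure measures f.

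Finally, the plan would expose a material effect through Supportive Estimand 2 and the table of mITT exclusions. That is true for TFC response, but only descriptively. For CGI-C the planned supportive estimand follows Supportive Estimand 1, which changes the population and the missing-data assumption together, so no version isolates the population effect.

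**Conclusion.** The mismatch is in the text and sits in the analyses that feed the hierarchy. It affects only composite failures with no post-baseline in-clinic TFC. The documents establish neither how many there will be nor in which arm.

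Under the assumed 2% against none and p = 0.5, the bias is about 1 percentage point before allowing for ET visits and about 0.2 points if 80% attend. It may favour pridopidine if such exits are more frequent on that arm, is zero if they are balanced with equal response rates, and can go the other way. This is a small but avoidable defect. Correcting it does not depend on knowing the direction.

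**What to change.** In Protocol 9.4.3 and SAP 7.4.2 and 7.4.3, state that for all binary endpoints every randomised and dosed participant who meets the composite non-response rule is kept in the main analysis set as a non-responder, whether or not a post-baseline TFC exists.

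For TFC response, the same result follows from making Supportive Estimand 2 (ITT, MAR) the main analysis and the mITT version supportive. Both are already planned. The downside is that a few participants are imputed from Baseline only.

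For CGI-C, apply only the retention rule. CGI-C has no Baseline value to impute from (only the modified CGI-S is collected then), and the stated MAR model is for TFC as a continuous variable. The retention rule does not bring back participants who left early for other reasons without a TFC, and the text should say so.

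The cost is a few sentences. Under SAP Section 5, a change before lock and unblinding goes in an Addendum. After unblinding it would have to be reported in the CSR as a change to the planned analyses.

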9.4.4. Exploratory Endpoints

The exploratory endpoints will be analyzed with methods similar to the primary and secondary endpoints. Additional details will be provided in the SAP.

9.4.5. Safety Analyses

The safety analysis will be conducted on the safety dataset. The AEs will be coded according to the Medical Dictionary for Regulatory Activities (MedDRA) dictionary. The TEAEs will be summarized by treatment group, system organ class and preferred term. Further summaries will be done by seriousness, severity and relationship to study drug.

Vital signs, ECG data and laboratory tests at Baseline at each post-baseline visit, and changes from Baseline to each of the post-baseline visits will be summarized with descriptive statistics. Shift tables for the laboratory tests based on a classification of values as low, normal, or high with respect to the reference range will be summarized.

For ECG data, absolute QTcF of > 450 ms, > 480 ms, and > 500 ms, changes from Baseline in QTcF > 30 ms and ≤ 60 ms, and changes in QTcF > 60 ms throughout the study will be summarized.

All other safety data will be summarized with descriptive statistics.

